4.1.5 Termination visit and safety follow-up visit - amended

A termination visit should be performed for patients who discontinue¹⁷ from study medication for any reason except death or lost to follow-up, and should occur as soon as possible after the patient receives his/her last dose of study drug. In general, at the Termination Visit the same safety and efficacy relevant measurements and procedures should be performed as at Visit 12. If the discontinuation occurs before Visit 8 (Week 14), the skin biopsy and the blood samples for biomarkers are to be collected. No blood samples for pharmacokinetics (PK) have to be taken and vital signs post dose are not needed because no new medication will be dispensed to the patient. If the Termination Visit will be performed after Visit 12 (Week 52) the patient's and physician's global assessment, patient interference with skin assessment, and tender and swollen joint count assessment must not be performed.

A safety follow-up visit (30 [+5] days after the last dose of study medication) will be performed for all patients.

If the patient discontinues study drug¹⁸ prematurely during the main treatment phase (Week 0 – Week 52) he/she will be invited to come for limited assessments (mRSS, pulmonary function test [FVC and DL_{CO} (diffusion capacity of the lung for carbon monoxide) including hemoglobin measurement at the local laboratory]¹⁹, patient-reported outcomes [PROs], and patient's and physician's global assessment²⁰) at Week 12, Week 26, Week 39, and Week 52, depending on the timing of discontinuation²¹. The collection of these assessments is important for endpoint analysis which considers all assessments post baseline up to Week 52.

A detailed schedule of evaluations is presented in Section 7.1.1.

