b Concomitant use of these medications will be allowed during the long-term extension phase⁵⁸

In addition, as described in Section 8.4.1 of the IB, "Interaction with other medicinal products and other forms of interaction", caution is advised during the intake of any of the following concomitant medications:

- The concomitant use of riociguat with strong multi-pathway cytochrome P450 (CYP) and P-glycoprotein 1 (P-gp)/breast cancer resistance protein inhibitors such as azole antimycotics (eg, ketoconazole, itraconazole) or human immunodeficiency virus protease inhibitors (eg, ritonavir) is not recommended, due to the pronounced increase in riociguat exposure.
- The concomitant use of riociguat with strong CYP1A1 (CYP family 1, subfamily A, polypeptide 1) inhibitors, such as the tyrosine kinase inhibitor erlotinib, and strong P-gp inhibitors, such as the immunosuppressive agent cyclosporine A, may increase

⁵⁵ Per Amendment 1

⁵⁶ Per Amendment 1

⁵⁷ Per Amendment 1

⁵⁸ Per Amendment 5

riociguat exposure. These drugs should be used with caution. Blood pressure should be monitored and dose reduction of riociguat considered.

Other medications and considerations (detailed information can be found in the current IB)

- Pre- and concomitant treatment with the proton pump inhibitor omeprazole (40 mg once daily) reduced riociguat mean area under the plasma concentration versus time curve (AUC) by 26% and mean maximum plasma concentration (C_{max}) by 35%. This is not considered clinically relevant.
- Co-administration of the antacid aluminum hydroxide / magnesium hydroxide reduced riociguat mean AUC by 34% and mean C_{max} by 56%. Antacids should be taken at least 1 hour after riociguat.
- Plasma concentrations in smokers are reduced by 50–60% compared with nonsmokers. For this reason, it is highly recommended to strongly advise patients to stop smoking while taking this medication⁵⁹. A dose reduction should be considered in patients who stop smoking whilst participating in the study.

Rescue⁶⁰ therapy

From Week 26 (Visit 10), patients with the following will have the opportunity to add rescue therapy to their randomized study medication. “Rescue therapy” is defined as treatment with an immunosuppressant drug, under the following situations:

- Worsening of skin disease (defined as >5 units and $\geq 25\%$ increase in mRSS), or

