- Relative decline in FVC % predicted by $\geq 10\%$, or relative decline in FVC % predicted between $\geq 5\%$ and $< 10\%$ with associated relative decline in DLco % predicted by $\geq 15\%$, provided that the decline in FVC results in FVC $< 75\%$ of predicted (confirmed by repeat pulmonary function testing within 1 month).

The decision to initiate rescue therapy is based on investigator discretion in eligible patients. Rescue therapy may include any of the following 4 agents: methotrexate, mycophenolate mofetil, cyclophosphamide, or azathioprine.

- Worsening of inflammatory joint disease or myositis.⁶¹

Rescue therapy can be initiated at investigator’s discretion in eligible patients. In addition to the 4 agents methotrexate, mycophenolate mofetil, cyclophosphamide, or azathioprine, hydroxychloroquine will be allowed for the treatment of inflammatory joint disease and myositis.⁶²

These treatments are not provided by the Sponsor.

A survey conducted by the Scleroderma Clinical Trials Consortium (SCTC) and Canadian Scleroderma Research Group (CSRG) to gain a consensus from SSc experts worldwide recommended these agents in the management of SSc after failure of first-line therapy.[19]

⁵⁹ Per Amendment 1

⁶⁰ Per Amendment 1– this footnote covers all changes in the section from escape to rescue

⁶¹ Per Amendment 5

⁶² Per Amendment 5

These agents also are featured in EULAR recommendations for the treatment of SSc[20] and in a recently published review of old and new therapies for SSc used in clinical practice.[21]

7. Procedures and variables

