8.4.2.1 Primary endpoint¹²¹

The primary analysis will be the change in mRSS from baseline to all assessments post baseline up to Week 52 using mixed model repeated measures (MMRM) with baseline mRSS as a covariate, fixed effects treatment arm and region, the interaction effect between study visit and treatment arm, and patient specific random effects to account for both heterogeneity among patients and correlation among measurements taken on the same patient with an unstructured covariance assumption. The main estimand of interest is the treatment difference

¹²⁰ Per Amendment 1

¹²¹ Per Amendment 4

between the riociguat and placebo treatment arms at Week 52. The null hypothesis to be tested is no difference between riociguat and placebo at this visit.

The model statement is:

$$Y_{ij} = \mu + \beta X_i + t_k + r_l + v_j + (tv)_{jk} + s_i + \varepsilon_{ij}$$

where Y_{ij} is the change from baseline in mRSS to visit j for subject i that is in treatment group k and region l ; μ is the intercept, β is the baseline covariate effect, X_i is the baseline mRSS for subject i , t_k is the fixed effect of treatment k , r_l is the fixed effect of region l , v_j is the fixed effect of visit j , $(tv)_{jk}$ is the interaction effect of treatment k by visit j , s_i is the random effect of subject i and $\varepsilon_{ij} \sim \text{Normal}(0, \sigma^2)$ represents the residual variance component with $\text{corr}(\varepsilon_{ij}, \varepsilon_{ij'}) = \rho_{jj'}$, $j \neq j'$

As a sensitivity analysis, the MMRM using the above model will also be applied to assessments post-baseline up to termination of study medication or initiation of rescue medication. In addition, the MMRM on all assessments will be repeated including additional effects time on rescue medication and time on study medication. MMRM assumes missing at random; mRSS by time of patient discontinuation from study medication¹²² will be summarized and further methods using multiple imputation that allow for missing data not at random will be investigated. Details of such methods will be described in the SAP.

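### The sensitivity MMRM that adjusts for time on rescue and time on study drug conditions on post-randomization consequences of treatment, so it is not a robustness check of the primary result

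*Protocol*

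**What the plan says.** Protocol 8.4.2.1 defines the primary analysis by its data: "The primary analysis will be the change in mRSS from baseline to all assessments post baseline up to Week 52". For the Week 52 contrast, "The null hypothesis to be tested is no difference between riociguat and placebo at this visit". Section 4.1.5 confirms that visits after stopping study drug are meant to be used: "The collection of these assessments is important for endpoint analysis which considers all assessments post baseline up to Week 52".

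Section 8.4.2.1 then lists sensitivity analyses. One is the same MMRM cut off at drug stop or start of rescue. The next is the model at issue: "the MMRM on all assessments will be repeated including additional effects time on rescue medication and time on study medication". After that, "further methods using multiple imputation that allow for missing data not at random will be investigated", with details left to the SAP. An ANCOVA at last visit, a stratified Wilcoxon test and an all-data endpoint analysis follow.

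The rescue rules are in section 6.9: "From Week 26 (Visit 10), patients with the following will have the opportunity to add rescue therapy to their randomized study medication". The first trigger opens "Worsening of skin disease (defined as >5 units and" and goes on to require a rise of at least 25% in mRSS. A decline in FVC, in some cases combined with DLco, is a second trigger. A third is "Worsening of inflammatory joint disease or myositis". Starting rescue is left to the investigator.

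Section 5.2.1.2 requires study drug to be stopped for unacceptable adverse events and allows it to be stopped for mRSS worsening. Section 7.3 lists need for rescue among the exploratory efficacy measures.

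For the model with the two added times, the protocol does not say how they are coded, whether they interact with arm, what effect is targeted, or how a difference from the primary result would be read. The SAP supplied covers only the long-term extension. The main-phase SAP it cites is not available here.

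**The concern.** A sensitivity analysis should vary an assumption and keep the target. This one changes the target. Time on rescue is partly a function of mRSS, and the trial itself treats need for rescue as an outcome. Time on study drug depends on tolerability, which can differ by arm, and on mRSS. Holding both fixed removes part of what treatment did and compares patients selected on how they fared. A single slope for time on study drug also pools time on placebo with time on riociguat.

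At stake is interpretation. If this output differs from the primary result, nobody can say whether the primary result is fragile or the two models answer different questions. If it agrees, the agreement is not evidence of robustness.

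**Working it through.** **1. The plan's own figure.** Section 8.6 uses a difference of 4, SD 8, two-sided 5% and 1:1 allocation. The normal approximation for 80% power gives n = 2 × (1.960 + 0.842)² × 8² / 4² = 62.8, so 63 per group. Exact noncentral-t power at 51, 53, 56, 58, 61 and 64 per group is 70.6, 72.2, 74.6, 76.1, 78.2 and 80.2%. Table 8-2 reproduces, and this point does not alter it. The documents give no figure for the adjusted model.

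**2. Why coding matters.** The extended model is the primary model plus γ₁ × (time on rescue) + γ₂ × (time on study drug).
- *Subject-total coding.* Each patient's final time on rescue enters the mean at every visit, including Weeks 12 and 26, before rescue can have acted. The model then conditions earlier outcomes on something those outcomes helped to cause.
- *Cumulative time to each visit.* If rescue depends only on mRSS already in the model, the MMRM can consistently estimate the effect without rescue. That is a legitimate estimand, but not the primary one. If rescue also depends on disease the model does not contain, this property is lost.

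**3. Size, by simulation.** From the documents: visits at Weeks 12, 26, 39 and 52, a Week 52 effect of −4, SD 8, and rescue from Week 26. Assumed, because the documents do not give them: SDs 4, 5.5, 7 and 8 across visits; correlation 0.8 to the power of the visit lag; placebo drift +1; a linear drug effect; 75% rescue uptake among eligible patients; a rescue effect of 0 or −3 points per 26 weeks; adverse-event stops of 5% versus 15% by arm; complete data; region omitted. The fit was an MMRM with unstructured covariance, baseline mRSS and treatment by visit, with 100,000 patients per arm. Simulation error per estimate is about 8 × √(2/100,000) = 0.04. Within a row, all models use the same data.

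Week 52 estimates:

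| Scenario | Primary | Both times, cumulative | Both times, subject total |
|---|---|---|---|
| A. mRSS-triggered rescue, inert | −3.95 | −3.94 | −3.36 |
| B. mRSS-triggered rescue, −3 | −3.69 | −3.97 | −3.10 |
| C. Rescue driven by disease not yet visible in mRSS, inert | −4.05 | −3.48 | −3.78 |
| D. As C, rescue −3 | −3.74 | −3.43 | −3.49 |
| E. As A, plus adverse-event and lack-of-efficacy stops | −3.64 | −3.72 | −3.15 |
| F. As B, plus the same stops | −3.38 | −3.71 | −2.92 |
| G. As D, plus the same stops | −3.45 | −3.33 | −3.24 |
| H. No effect of any kind, equal stopping | 0.01 | 0.01 | 0.03 |
| I. No mRSS effect, adverse-event stops differ | −0.01 | −0.01 | −0.16 |

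In A to D nobody stops drug, so time on drug adds nothing beyond visit and the shift comes from time on rescue alone.

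**4. Reading the table.**
- Subject-total coding attenuates in every row with a real effect (A to G), by 3.45 − 3.24 = 0.21 (G) up to 3.95 − 3.36 = 0.59 (A, 15%) and 3.69 − 3.10 = 0.59 (B, 16%).
- Cumulative coding ranges from no material shift (A, 0.01), through attenuation of 4.05 − 3.48 = 0.57 (C, 14%), to a larger effect by 3.71 − 3.38 = 0.33 (F, 10%).
- In B, cumulative coding recovers the no-rescue effect: −3.97 against −4.
- In F, the effect without rescue but with stopping is about −3.64 (row E, primary), and with neither it is −4. The cumulative estimate of −3.71 matches neither exactly.
- With 64 per arm and 500 runs, rejection in row I was 5.6% for the primary model and 6.0% and 6.2% for the adjusted ones. In row A, power was 79.0% for the primary model and 72.8% with subject-total coding. Monte Carlo error is at most about 2 percentage points.

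**The case against.** The strongest reply is that the model can be right for a sensible question. With cumulative coding and rescue driven only by recorded mRSS, it returns the effect without rescue (row B), which the primary analysis does not. So a reader who infers that the adjusted coefficient is always biased goes too far. So does one who infers that it always pulls towards zero: rows E and F move the other way. Nor does any distortion appear when treatment affects neither mRSS nor the two times (row H).

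It is also tempting to size the problem with a Week 52 ANCOVA that adds time on rescue. That is not the protocol's model. It leaves out the Week 26 mRSS that triggers rescue and omits time on study drug, so its attenuation cannot be carried over to the MMRM.

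Further, this is one supportive analysis among several, and the main-phase SAP may state the coding and the intended reading.

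All of that stands, and it narrows the point. It does not remove it. Section 6.9 also allows rescue for lung decline, joint disease and myositis, at the investigator's discretion, and none of these is in the mRSS model. The favorable condition is therefore doubtful here, and rows C and D show cumulative coding missing both targets when it fails. Even where the condition holds, the result answers a different question from the primary analysis.

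**Conclusion.** The point holds in a limited form. The coefficient from this model generally estimates neither the primary all-assessments effect nor, outside special conditions, the effect without rescue. Under the assumed inputs the shift from the primary estimate is 0 to about 0.6 of a 4-point effect. It is attenuation with subject-total coding and goes either way with cumulative coding. The sizes depend on correlations, rescue uptake, rescue effect and stopping rates that the documents do not give.

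A reader might infer that the primary result is itself compromised. The documents do not support that. The primary MMRM excludes these terms, and its test, alpha, the testing hierarchy and the sample size are untouched. This is a flaw of interpretation in one supportive analysis, worth correcting because the remedy is cheap.

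**What to change.** Do not use this model as a robustness check of the primary result. Either drop it or relabel it exploratory, stating the coding of both times, any interaction with arm, and that it does not target the primary estimand. Amendment 7 says it was prepared on the main-phase results, so if the output already exists, relabeling is more transparent than removal.

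Address rescue and discontinuation with methods already in section 8.4.2.1:
- Keep the truncated MMRM, and name its estimand: the effect had patients neither stopped drug nor taken rescue, under missing at random.
- Make the planned multiple imputation specific. Set mRSS after rescue or drug stop to missing and impute it under stated reference-based assumptions, and under delta-adjusted assumptions carried to a tipping point. Name the estimand of each. Imputation under missing at random alone would largely repeat the truncated MMRM.
- Present these beside the primary all-assessments MMRM, with one sentence on how a difference would be read.

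The cost is SAP wording, some programming and the loss of one supportive output. No extra data or patients are needed.

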8.4.2.2 Secondary and exploratory endpoints¹²⁷

General aspects

The other secondary and exploratory efficacy variables measured on a continuous or semi-continuous scale will be analyzed using the MMRM, ANCOVA, and stratified Wilcoxon test, as for the mRSS above.

The time to first mRSS progression and regression and clinical outcome parameters will be analyzed using the log-rank test comparing between treatment groups.

Any binary outcomes, such as the predicted CRISS outcome, will be analyzed using Mantel-Haenzel weights, stratified by region. Also as a sensitivity analysis in addition to the time to event analysis, the occurrence of the events mRSS progression and regression and clinical outcome parameters will be analyzed using this method.

Details on any descriptive subgroup analyses will be specified in the SAP. These will include gender and region.

Hierarchical testing of secondary endpoints¹²⁸

The following secondary endpoints will be tested in a hierarchical fashion at a 2-sided 5% level, only if the primary endpoint of mRSS is shown to be statistically significant at a 2-sided 5% level.

The following order of testing will be applied:

- CRISS
- HAQ-DI (health assessment questionnaire-disability index)
- Patient's global assessment
- Physician's global assessment
- FVC % predicted

For example, if CRISS is statistically significant at a 2-sided 5% level, then the HAQ-DI will be tested, if not the testing procedure will be stopped. This step is repeated further down the list of the 5 secondary endpoints until a non-statistically significant endpoint is reached.

These particular secondary endpoints were chosen to be tested in this hierarchical fashion, because the mRSS and the above additional, secondary variables were considered to have the greatest face validity when designing the CRISS [41].

¹²⁷ Per Amendment 4

¹²⁸ Per Amendment 4

American College of Rheumatology Combined Response Index for Systemic Sclerosis¹²⁹

The key secondary endpoint will be the CRISS at Week 52.¹³⁰

Application of CRISS algorithm in a randomized clinical trial is a 2-step process. Firstly, evaluate if patients have met the criterion for not-improved. If yes, these patients are assigned a probability score of 0.0. For the remaining patients, calculate the probability based on change in 5 measures: mRSS, FVC %, HAQ-DI, patient's global assessment, and physician's global assessment, where each measure has a probability score between 0 and 1 [41].

In Step 1, a patient is clinically evaluated to determine whether the patient has improved or not. Expert consensus on the definition of a patient who is not improved during a trial is the following:

A patient is considered not improved and is assigned a probability score of improving equal to 0.0, irrespective of improvement on other core items, if he/she develops:

1. New scleroderma renal crisis,
2. Decline in FVC % predicted $\geq 15\%$ (relative), confirmed by another FVC % within a month, high resolution computed tomography (HRCT) to confirm interstitial lung disease (if previous HRCT did not show interstitial lung disease) and FVC % predicted below 80% predicted (attributable to SSc),
3. New onset of left ventricular failure (defined as ejection fraction $\leq 45\%$) or new onset of pulmonary arterial hypertension requiring treatment (attributable to SSc).

If the patient is determined to exhibit improvement in Step 1 (ie, not assigned a 0.0), Step 2 involves computing the predicted probability of improving (a score between 0.0 and 1.0, inclusive) for each patient using the equation:

$$\frac{\exp[-5.54 - 0.81 * \Delta_{MRSS} + 0.21 * \Delta_{FVC\%} - 0.40 * \Delta_{Pt-glob} - 0.44 * \Delta_{MD-glob} - 3.41 * \Delta_{HAQ-DI}]}{1 + \exp[-5.54 - 0.81 * \Delta_{MRSS} + 0.21 * \Delta_{FVC\%} - 0.40 * \Delta_{Pt-glob} - 0.44 * \Delta_{MD-glob} - 3.41 * \Delta_{HAQ-DI}]}$$

where Δ_{MRSS} indicates the change in mRSS from baseline to Week 52, Δ_{FVC} denotes the change in FVC % predicted from baseline to Week 52, $\Delta_{Pt-glob}$ indicates the change in patient global assessment, $\Delta_{MD-glob}$ denotes the change in physician global assessment, and Δ_{HAQ-DI} is the change in HAQ-DI¹³¹. Note that all changes are absolute changes ($Time_2 - Time_{baseline}$) and that the physician's and patient's global assessment was measured on the Likert scale ranging from 0 to 10, where 0 = excellent, and 10 = extremely poor.

Hence, the CRISS is comprised of 5 variables: mRSS, FVC % predicted, patient's global assessment, physician's global assessment, and HAQ-DI from the SHAQ patient reported outcome. Combined, the 5 variables explained 89.3% of the variability in the data.

Individually, when used in a single-variable logistic regression model, mRSS explained 66.3% of the variation, FVC % predicted explained 36.1% of the variation, physician global assessment explained 24.5% of the variation, patient global assessment explained 23.7% of the variation, and HAQ-DI explained 28.5% of the variation. A change in mRSS, FVC % predicted and HAQ-DI are strong indicators of whether a patient is likely to be improved or not. In each scenario, a decrease of mRSS or HAQ-DI from baseline to Week 52¹³² and an

¹²⁹ Per Amendment 4

¹³⁰ Per Amendment 5

¹³¹ Per Amendment 5

¹³² Per Amendment 5

increase in FVC % predicted corresponds to very high probabilities of improving. For patient's global and physician's global assessment, the association between probability of improving and change in these 2 core components is less evident. Subjects for which the predicted probability is greater or equal to 0.60 are considered improved, while subjects for which the predicted probability is below 0.60 are considered not improved. The 2 groups (riociguat vs. placebo) can then be compared in a 2x2 table using appropriate significance tests. The predicted probabilities obtained using the CRISS can also be assessed as a continuous variable and the distributions of the probability of improving for patients on drug vs. placebo can be compared using non-parametric tests [41]. In this study, the CRISS outcome will be analyzed using Mantel-Haenzel weights, stratified by region, and additionally, the stratified Wilcoxon test will be used as non-parametric test.

However, Step 2 assumes that there is complete data; ie, all 5 components of the CRISS are fully recorded at Week 52. If the subject discontinues from study drug before Week 52, or has one or more missing components of the CRISS at this visit, then a mixed model repeated measures (MMRM) analysis will be implemented to estimate the value or values for those components at Week 52. These estimates will then be used to calculate the CRISS score at Week 52 as given in Step 2. Subjects for which the predicted probability is greater or equal to 0.60 are considered improved, while subjects for which the predicted probability is below 0.60 are considered not improved. [41] Further details will be provided in the statistical analysis plan.

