7.1.2.10 Premature discontinuation of study drug treatment - amended

In the event of premature discontinuation of study drug treatment, patients must undergo the same procedures as outlined for the termination visit (Section 7.1.2.8) and then undergo evaluation at the safety follow-up visit, 30 (+5) days later (Section 7.1.2.9).

The reason for premature discontinuation of study drug treatment or early withdrawal from the study must be recorded in the eCRF (please refer to Section 5.2).

If the patient discontinues study drug⁹¹ prematurely during the main treatment phase (Week 0 – Week 52) he/she will be invited to come for limited assessments (mRSS, pulmonary function test [FVC and DL_{CO} including hemoglobin measurement at the local laboratory]⁹², PROs, and patient's and physician's global assessment)⁹³ at Week 12, Week 26, Week 39 and Week 52, depending on the timing of discontinuation⁹⁴. This will be in addition to the termination visit assessments (see Section 7.1.2.8), provided that the patient does not object to collection of study data after withdrawal of consent. If the discontinuation occurs before Visit 8 (Week 14), a skin biopsy will also be performed.

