7.6.15 Patient's and physician's global assessment - amended

This tool incorporates a self-assessment and physician assessment on the patient's overall health in the prior 1 week using a 0–10 ordinal scale and a rating of overall SSc-related health transition compared with 1 month prior and 1 year prior.

Frequency: Visit 1 (Day 0), Visit 10 (Week 26) and Visit 12 (Week 52), termination visit (not needed after V12), and visits with limited assessments.¹¹⁸

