- Additionally, the sponsor for US territory was added. Bayer HealthCare Pharmaceuticals Inc. is and has been the sponsor for the US territory for this study as set forth in FDA Investigational New Drug (IND) form 1571. The reference on the protocol was incomplete in this regard.

Further changes to the protocol included the following clarifications and additions:

- Update of permitted concomitant medication during the long-term extension phase.
- Update of allowed rescue therapy.
- Clarification that biomarker analyses will be reported separately.
- Addition of description of unblinding process for biomarker and PK analysis.

- Clarification of sampling time points for blood samples for PK analysis and documentation requirements.
- Addition of analysis of PK data in relationship of exposure parameters with treatment effects.
- Change in time point for first data cleaning and reporting.
- Clarification for adverse event reporting regarding conditions of SSc.
- Clarification of the wording for exclusion criterion 5.
- Addition of one criterion for discontinuation of the study medication in case patients develop renal disease and hepatic insufficiency in alignment with exclusion criteria 2 and 3.
- Addition of the patient's and physician's global assessment to the visits with limited assessments to ensure that all required variables are available at Week 52 for the analysis of the CRISS.
- Correction of visit window for Visit 18.
- Clarification of allowed dose interruptions in the open-label extension period.

Correction of typographical errors and minor editorial changes are not specified in the list of changes below. New text is displayed as underlined; text that was deleted is presented as strike-through text.

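### CRISS at Week 52: the protocol scores model estimates against the 0.60 cut as if observed, which distorts responder rates and understates the standard error, and its trigger for estimation is ambiguous

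*Protocol*

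**What the plan says.** Protocol 8.4.2.2 makes CRISS the key secondary endpoint and the first tested after mRSS. Step 2 turns five Week 52 changes (mRSS, FVC % predicted, HAQ-DI and the two global assessments) into a probability. A patient at 0.60 or above counts as improved.

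For incomplete data, the section starts MMRM estimation "If the subject discontinues from study drug before Week 52, or has one or more missing components of the CRISS at this visit". It then says: "These estimates will then be used to calculate the CRISS score at Week 52 as given in Step 2". The same 0.60 cut follows. The improved/not-improved outcome is compared with Mantel-Haenszel weights by region and, "additionally, the stratified Wilcoxon test will be used as non-parametric test". The passage closes with a deferral: "Further details will be provided in the statistical analysis plan".

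Patients who stop drug are still followed. Protocol 7.1.2.10 says that "he/she will be invited to come for limited assessments (mRSS, pulmonary function test" and goes on to list patient-reported outcomes and both globals, at Weeks 12, 26, 39 and 52. Section 7.6.15 schedules the globals at the "termination visit (not needed after V12), and visits with limited assessments". HAQ-DI comes from the SHAQ (7.6.13), so all five components are collected. Section 4.1.5 gives the reason: "The collection of these assessments is important for endpoint analysis which considers all assessments post baseline up to Week 52". The Amendment 5 overview (13.3.1) says the globals were added "to ensure that all required variables are available at Week 52 for the analysis of the CRISS".

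**The concern.** There are two problems.

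**Method.** A model estimate of a patient's Week 52 value is a predicted mean. Predicted means are less spread out than real outcomes. Passing them through a fixed cut moves patients to whichever side of 0.60 their predicted mean lies on, so the responder proportion in each arm is distorted. Counting them as observed also claims more information than exists, so the standard error is too small. Section 8.4.2.1 names multiple imputation for mRSS sensitivity analysis; 8.4.2.2 describes nothing of the kind for CRISS. The additional Wilcoxon test avoids the 0.60 cut but uses the same estimates.

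**Trigger.** The word *or* makes stopping study drug sufficient for estimation, even when all five components were measured at the Week 52 limited visit. That does not fit the purpose stated in 13.3.1, or the primary analysis, which uses all post-baseline assessments.

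At stake are the responder difference and its interval for the key secondary endpoint, which readers will use directly.

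**Working it through.** **The plan's own figure.** No power figure is given for CRISS. For mRSS, Table 8–2 (difference 4, SD 8, two-sided 5%) reproduces with the noncentral t distribution: 70.6% power at 51 per group and 80% at 64.

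**Inputs from the protocol.** CRISS coefficients and the 0.60 cut (8.4.2.2); SD 8, difference 4 and 64 per arm (8.6).

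**Assumed, not in the documents.** Share estimated: 10–20% per arm, up to 30% in one arm. R-squared, the share of Week 52 variance that earlier data predict: 0.25–0.75. Mean mRSS changes −6 and −2. Only mRSS varies between patients.

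**Threshold on mRSS.** The linear predictor must reach ln(0.6/0.4) = 0.405.
- Other components unchanged: fall of (5.54 + 0.405)/0.81 = 7.34.
- HAQ-DI down 0.25 and both globals down 1: (5.54 + 0.405 − 3.41×0.25 − 0.40 − 0.44)/0.81 = 5.25.

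**Responder share.** True: Φ((−T − mean)/8). From estimates: Φ((−T − mean)/(8√R²)).
- T = 7.34, mean −2: true 25%; estimated 9%, 17%, 22% at R² 0.25, 0.50, 0.75.
- T = 5.25, mean −8: true 63%; estimated 75%, 69%, 65%.

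The direction therefore depends on where the mean sits relative to the cut.

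**Treatment difference (percentage points).** Example at T = 7.34, R² = 0.25: true 43.3 − 25.2 = 18.1; from estimates 36.9 − 9.1 = 27.8; with 10% estimated in each arm, 0.9×18.1 + 0.1×27.8 = 19.1.

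| T (true difference) | R² | 10/10 | 20/20 | 30/10 | 10/30 |
|---|---|---|---|---|---|
| 7.34 (18.1) | 0.25 | 19.1 | 20.1 | 17.8 | 22.3 |
| | 0.50 | 18.7 | 19.2 | 18.1 | 20.2 |
| | 0.75 | 18.3 | 18.6 | 18.1 | 19.0 |
| 5.25 (19.5) | 0.25 | 21.2 | 22.9 | 22.0 | 23.9 |
| | 0.50 | 20.3 | 21.0 | 20.6 | 21.4 |
| | 0.75 | 19.8 | 20.1 | 19.9 | 20.2 |

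Columns give the percentage estimated, riociguat/placebo.

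**Coverage of a nominal 95% interval.** Simulation: T = 7.34, one earlier value as predictor, missing at random, unstratified risk difference.

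| Estimated per arm | R² 0.25 | R² 0.50 | R² 0.75 |
|---|---|---|---|
| 10% | 92.4% | 93.1% | 93.5% |
| 20% | 89.9% | 92.1% | 93.1% |

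Independent repeats stayed within about 92–94% and 88–93%. With all data observed, coverage is 94.1–94.8%; with multiple imputation, 94.9–96.4%. At 20% estimated and R² 0.25, the reported standard error is 0.080 against an actual SD of 0.092.

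**All five components varying.** A separate simulation, with further assumed SDs and correlations and 20% missing, gave coverage of 84.8–93.1% in its three non-null settings, and 94–95% with multiple imputation in the two settings where that was run. The mean shift in the difference ran from −0.5 to about +5 points.

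**Null case.** With no mRSS effect and only mRSS varying, the stand-alone CRISS test rejects in 6.1–9.4% of runs. With the mRSS gate the figure is 2.1–3.1%. For the Wilcoxon test the figures are 5.7–10.7% stand-alone and 4.1–4.7% gated.

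**The case against.** **The details may be elsewhere.** Section 8.4.2.2 defers to the SAP. The supplied SAP covers only the extension; its introduction cites main-phase SAP version 4.0, finalised before unblinding, which may specify draws or another rule. This stands as a limit. It does not remove the problem in the protocol text, which states how the estimates are used and mentions no draw or variance step.

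**The trigger has a benign reading.** The preceding sentence is about incomplete data, and the components to be estimated can be taken as the missing ones only. The clause came with Amendment 4, before the limited visits included the globals, so it may be leftover wording. This also stands. A reader might infer that observed off-drug data are discarded; the documents do not establish that. Even on the literal reading, an observed value could still inform the estimating model. What remains is a sentence with two readings.

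**The effect can be small.** At 10% estimated per arm the shift is 0.2–1.7 points, against a standard error of about 8 points. If most patients who stop drug return at Week 52, fewer values need estimating.

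**The simulation simplifies the plan.** It is unstratified, uses one predictor and varies mRSS alone. The 95% interval is specified under the primary endpoint (8.4.2.1), not separately for CRISS. The figures therefore show the order of magnitude and do not forecast the result.

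**Conclusion.** The concern holds for the protocol as written. Cutting model estimates at 0.60 and analysing them as observed distorts responder proportions and makes the standard error too small. Under the assumptions above, coverage is about 92–94% with 10% estimated and 88–93% with 20%. The difference shifts by 0.2–1.7 points at 10% per arm, and by up to about 4 points when 20% or more is estimated in at least one arm and prediction is poor. The direction is not fixed by the documents, and the shift is small when earlier visits predict Week 52 well.

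A reader might infer that the testing procedure exceeds 5%. That is not supported: CRISS is tested only after a significant mRSS result, so with no mRSS effect the gate holds joint rejection below 5%. The harm is to the reported estimate and interval.

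The trigger needs clarifying and carries no size of its own. Version 4.0 may already settle both points.

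**What to change.** (a) Make a missing Week 52 component the only trigger, and state that observed Week 52 components are used whether the patient is on or off drug.

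(b) Multiply impute only the missing components, jointly and with residual error. Compute CRISS and apply the 0.60 cut in each completed data set, and combine the Mantel-Haenszel differences by Rubin's rules.

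If main-phase SAP version 4.0 already does this, align 8.4.2.2 with it. If not, leave the planned analysis in place and report (a) and (b) together as a labelled supplementary analysis beside it. The Amendment 7 rationale shows that main-phase results already exist, so the prespecified rule should not be replaced now.

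The cost is a short clarification in 8.4.2.2 and moderate analysis work, with no new visits or procedures. Nominal CRISS power falls somewhat. In the mRSS-only simulation it was 51–59% with multiple imputation, 60–61% with all data observed and 62–67% with single estimates; part of that last figure comes from the too-small standard error.
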